6.2.3 Clinical laboratory variables

6.2.3.1 Potentially Clinically Significant (PCS) Laboratory Criteria

Laboratory test values are potentially clinically significant (PCS) if they meet either the low or high PCS criteria listed in [Table 7](#) below.

Table 7 Potentially Clinically Significant (PCS) Laboratory Criteria

Potentially Clinically Significant Laboratory Criteria			
Laboratory Parameter	Unit	Low PCS Criteria	High PCS Criteria
Alanine Aminotransferase (ALT)	U/L	no lower limit	> 3X ULN > 5X ULN [#] > 8X ULN [#] > 10X ULN [#] > 20X ULN [#]
Aspartate Aminotransferase (AST)	U/L	no lower limit	> 3X ULN > 5X ULN [#] > 8X ULN [#] > 10X ULN [#] > 20X ULN [#]
Alkaline Phosphatase (ALP)	U/L	no lower limit	> 1.5 X ULN [#] > 3 X ULN
ALT or AST	U/L for ALT or AST	no lower limit	ALT or AST > 8X ULN
Total Bilirubin	µmol/L	no lower limit	> 1.5 X ULN > 2 X ULN [#]
Moderate Liver Abnormality**	U/L for ALT and AST, µmol/L for Total Bilirubin	no lower limit	ALT and/or AST > 3X ULN or Total Bilirubin > 2X ULN
Severe Liver Abnormality**	U/L for ALT and AST, µmol/L for Total Bilirubin	no lower limit	ALT and/or AST > 3X ULN and Total Bilirubin > 2X ULN
Gamma Glutamine Transaminase (GGT)	U/L	no lower limit	> 3X ULN
Calcium	mmol/L	< 0.8 X LLN	>1.2 X ULN
Creatinine	µmol/L		>1.5 X Baseline
Potassium	mmol/L	< 0.75 X LLN	>1.2 X ULN
Sodium	mmol/L	< 0.9 X LNL	>1.1 X ULN
Total Protein	g/L	< 0.9 X LNL	>1.1 X ULN
Blood Urea Nitrogen (BUN)	mmol/L		>1.5 X Baseline
Neutrophils	10 ⁶ /L	≤1000	
Platelet Count	10 ⁹ /L	≤100	≥700
White Blood Cell Count	10 ⁹ /L	≤2.5	≥15
Triacylglycerol/Lipase	U/L	no lower limit	> 3X ULN or > 2 X Baseline
LLN: Lower limit of normal, value provided by the laboratory ULN: Upper limit of normal, value provided by the laboratory			

*Hemoglobin in SI unit (for conventional unit g/dL, divide by 10)

** a subject's ALT and Total Bilirubin laboratory draw date or AST and Total Bilirubin laboratory draw date must occur on the same blood sample in order to be counted.

[#] Additional criteria required for summary of Liver Function Tests only (see Section [7.5.2.1](#))

Potentially Clinically Significant Laboratory Criteria will be calculated at each study visit and on-treatment (see Section [6.2](#)) using the worst value among all available measurements,

except for Moderate and Severe Liver Abnormalities which will be calculated on-treatment only.

Time to occurrence of an abnormality (for selected criteria)

Time to occurrence of an abnormality, will be derived only for the following PCS criteria:

- Hemoglobin <6 g/dL
- Hemoglobin >14 g/dL
- Alanine Aminotransferase (ALT) > 3X ULN
- Aspartate Aminotransferase (AST) > 3X ULN
- Total Bilirubin > 1.5 X ULN

For each potentially clinically significant laboratory criteria, the time to occurrence of an abnormality for a subject with an abnormality at any moment during the Safety Emergent Period (see Section 6.2) will be calculated (in years) as defined in Section 6.2.2

Time to censoring will be defined (in years) as :

(Date of last laboratory assessment where parameter analyzed is non-missing during the Safety Emergent Period – Analysis date of first dose intake +1) / 365.25

6.2.3.2 Laboratory assessments

For all laboratory parameters, the minimum and the maximum values on treatment (see Section 6.2) will be defined.

In addition, each laboratory result will be classified as low (L), normal (N), or high (H) at each visit according to the laboratory supplied reference ranges.

Change from baseline will be calculated as the measurement taken at the specific visit minus the measurement at baseline visit.

Baseline assessment is the assessment from the day 1 visit, except for Hb (see Section 6.1.1).

If Day 1 is missing, the screening or unscheduled assessment that is closest prior to Day 1 will be used.

Screening is defined as the screening or unscheduled assessment that is closest to Day 1.

For the lipid panel and glucose parameter, two baseline values will be defined based on fasting status: regardless of fasting and fasted.

6.2.4 Physical Examination

A comprehensive physical examination will be conducted during the screening period and at the EOT visit and recorded in the source documents. This examination will include general appearance and the following body regions and systems: head, eyes, ears, neck and throat (HEENT), lungs, heart, chest and back, abdomen, genitourinary, extremities, skin and any other, if deemed necessary.

A targeted examination (e.g., respiratory and cardiovascular) will be conducted and recorded in the source documents.

Only the date of the physical examination will be recorded in the eCRF. There will be no table or listing for the physical examination. Any clinically relevant adverse change will be recorded as an AE in the eCRF.

6.2.5 12-lead Electrocardiogram (ECG)

The 12-lead ECG measurements will be performed on all subjects at specific times. A single ECG measurement will be taken with the subject in the supine position, after the subject has been lying quietly for 5 minutes. Clinically significant abnormalities will be reported as an AE.

The visit, ECG date, Pulse, RR Interval, PR interval, QRS Interval, QT Interval, overall interpretation and relevant comments will be recorded in the eCRF.

Baseline assessment is the assessment from day 1 visit. If day 1 assessment is missing, screening period assessment will be used in the analysis.

QTc interval will be calculated using both

- Bazett ($QTcB = QT/(RR \text{ Interval})^{1/2}$) and
- Fridericia ($QTcF = QT/(RR \text{ Interval})^{1/3}$) corrections,

where QT is in msec and RR Interval in seconds; and if RR Interval is not available, it will be replaced with 60/HR.

For all ECG parameters, the maximum post-baseline value on treatment will be defined (see Section 6.2).

ECG values are potentially clinically significant (PCS) if they meet or exceed the upper limit values listed in Table 8 below.

Table 8 ECG Parameters classification

ECG Parameter	Classification
QTc interval (msec)	> 450 msec, > 480 msec, > 500 msec;
QTc interval change (msec)	> 30 msec and > 60 msec (increase from baseline)
QRS (msec)	≥ 150 msec
PR (msec)	≥ 250 msec

Time to occurrence of PCS ECG :

For the two QTc criteria ($QTc > 500$ msec ; change from baseline in $QTc > 60$ msec), the time to occurrence (in years) for a subject with occurrence of the PCS at any moment during Safety Emergent Period (defined in Section 6.2) will be calculated (in years) as defined in Section 6.2.2

Time to censoring will be defined as :

(Date of last ECG assessment where parameter analyzed is non-missing during the Safety Emergent Period – Analysis date of first dose intake +1) / 365.25

6.2.6 Vascular Access Thrombosis (VAT)

For each AE listed as VAT, additional information regarding the event will be recorded.

6.3 Pharmacokinetic Variables

All details of the population PK analysis will be described in a separate analysis plan.

6.4 Pharmacodynamic Variables

Not applicable.

6.5 Other Variables

6.5.1 Eligibility criteria

Eligibility at screening will be recorded as a yes/no variable for each criterion. The date of the informed consent for the subjects will also be documented.

6.5.2 Demographic and Baseline Characteristic Variables

Demographic characteristics will be recorded at screening (sex, the day, month and year of birth, age, race, height and weight).

Collection of date of birth depends on local regulations. Day of birth will be recorded in the eCRF as the first of the month when the day is not allowed to be collected. In cases where only year of birth is allowed to be collected, day and month will be recorded in the eCRF as the first of January. Age will be recalculated in SDTM and ADAM datasets.

If D_B is the Date of Birth and D_{First} is the Date of First Dose intake, Age is $Age = (D_{First} - D_B + 1) / 365.25$. If the Date of First Dose intake is not available, Date of Informed Consent will be used.

Based on recalculated age, three categories will be defined:

- < 65 years
- 65 - 74 years,
- ≥ 75 years

Each subject's body mass index (BMI) will be calculated as:

$$BMI (Kg/m^2) = Weight (Kg) / [Height (m)]^2,$$

in which the height will be converted from cm. into m. by dividing by 100.

Tobacco history and use will be recorded at screening.

The average maximum quantity of tobacco per week will be calculated using the average maximum quantity and frequency filled in the CRF. If the frequency is “Day”, the average maximum quantity of tobacco per week will be determined as follows:

$$\text{average maximum quantity per day} \times 7$$

If the frequency is “/Month”, the average maximum quantity of tobacco per week will be determined as follows:

$$\text{average maximum quantity per month} / 4.3482$$

Screening Hb will be defined as the mean of the three latest central laboratory Hb values prior to the day of randomization.

Baseline Hb is defined in Section [6.1.1](#)

Based on the mean screening Hb value, two categories will be defined:

- ≤ 8.0 g/dL
- > 8.0 g/dL

History of cardiovascular, cerebrovascular or thromboembolic diseases at baseline will be determined by performing a medical review of preferred terms recorded on any of the medical history forms. . History will be categorized as:

- Yes
- No

Countries and Regions

Subjects will be enrolled from the following countries:

Region A (Western Europe)

- Spain
- UK
- Italy
- Belgium

Region B (Rest of the World)

- Bulgaria
- Hungary
- Russia
- Romania
- Poland
- Turkey
- South Africa
- Serbia
- Ukraine
- Georgia

- Estonia
- Greece
- Panama
- Peru
- Guatemala
- Columbia
- Dominican Republic
- Belarus

Region B includes additional countries which were not part of the initial list of countries from Central and Eastern Europe as per IRT due to extended recruitment in Central and South Americas as well as Africa.

Randomization will be stratified by region using two categories:

- Region A: Western Europe
- Region B: Rest of the World

A limited amount of subjects is expected to be recruited out of Europe and will be randomized under the Central and Eastern Europe level of the Interactive Response Technology .

Time to Treatment Discontinuation

Time to Treatment Discontinuation in years is defined as:

Time to Treatment Discontinuation (years) = ('Date of Treatment Discontinuation - ('Analysis date of first dose intake +1)/365.25

In case a subject completed the treatment period, time to censoring will be calculated as :

(Analysis date of last dose – Analysis date of first dose intake + 1) / 365.25

With Analysis data of last dose defined in Section [6.5.4](#)

Time in years from Diagnosis of Anemia

Time from diagnosis of anemia in years is defined as:

Time from Diagnosis of Anemia (years) = ('Analysis date of first dose intake '-'Date of Diagnosis')/365.25

In case of partial dates, imputation rules apply and are detailed in Section [7.11.2](#)

Time in years from Diagnosis of CKD

Time from diagnosis of CKD in years is defined as:

Time from Diagnosis of CKD (years) = ('Analysis date of First Dose intake '-'Date of Diagnosis of CKD')/365.25

In case of partial dates, imputation rules apply and are detailed in Section [7.11.2](#)

Time from Diagnosis of Targeted Medical History

Onset date and the start date of analysis for the study drug are collected and the time from diagnosis of targeted medical history in years is defined as

$$\text{Time from Diagnosis of Targeted Medical History (years)} = (\text{'Analysis date of first dose intake'} - \text{'Onset Date'}) / 365.25$$

In case of partial dates, imputation rules apply and are detailed in Section [7.11.2](#)

This will be calculated for each patient who was diagnosed with the targeted medical history: hypertension, diabetes mellitus type 1, type2 and combined, dyslipidemia and vascular access.

eGFR

eGFR will be provided by the central laboratory only for the selected visits as described in the schedule of assessments. It will be calculated by the central lab using the following 4-variable Modification of Diet in Renal Disease (MDRD) equation:

$$\text{eGFR (in mL/min per 1.73m}^2\text{)} = 175 \times (\text{SCr in mg/dL})^{-1.154} \times (\text{Age in years})^{-0.203} \\ \times (0.742 \text{ if female}) \times (1.21 \text{ if African American})$$

where SCr = serum creatinine concentration.

Since SCr will be collected for all the selected visits above plus additional ones, eGFR will be derived using the same formula and the derived eGFR will be used for the analysis. Checks will be performed by programming in order to ensure that derived eGFR values will match with eGFR provided by ICON for the selected visits.

Screening eGFR will be classified in the following categories : < 30 mL/min/1.73 m² versus ≥ 30 mL/min/1.73m², and <10, 10-<15, 15-<30, 30-<45, 45-<60, and ≥60 mL/min/1.73m²

Iron Repletion at Screening

Subjects will be classified in one of the following four groups according to the TSAT and ferritin levels collected at Screening (prior to first drug intake):

- ferritin < 30 ng/mL or TSAT < 5%
- 30 ≤ ferritin < 100 ng/mL and 5% ≤ TSAT < 20%
- 30 ≤ ferritin < 100 ng/mL and TSAT ≥ 20%
- ferritin ≥ 100 ng/mL and 5% ≤ TSAT < 20%
- ferritin ≥ 100 ng/mL and TSAT ≥ 20%

Regarding Iron Repletion at screening, both TSAT and Ferritin should be coming from the same blood sample in cases that we have more than one record.

Iron Repletion at Baseline

Subjects will be classified in one of the following four groups according to the TSAT and ferritin levels collected on Day 1:

- ferritin < 30 ng/mL or TSAT < 5%
- $30 \leq \text{ferritin} < 100 \text{ ng/mL}$ and $5\% \leq \text{TSAT} < 20\%$
- $30 \leq \text{ferritin} < 100 \text{ ng/mL}$ and $\text{TSAT} \geq 20\%$
- ferritin $\geq 100 \text{ ng/mL}$ and $5\% \leq \text{TSAT} < 20\%$
- ferritin $\geq 100 \text{ ng/mL}$ and $\text{TSAT} \geq 20\%$

Regarding Iron Repletion at baseline, both TSAT and Ferritin should be coming from the same blood sample in cases that we have more than one record on Day 1. If no Day 1 assessment is available, Iron Repletion at Screening will be used.

Use of ESAs during the last year prior to start of study treatment

Subjects will be classified as either having used or not ESAs during the last year. Previous use of ESAs is collected in the Treatment History for Anemia Form.

6.5.3 Previous and concomitant medication

Previous medication is defined as a medication with at least one dose taken before the date of first dose of study drug.

Concomitant medication is defined as a medication with at least one dose taken between the date of first dose (inclusive) and the date of the End of the Safety Emergent Period.

Previous and concomitant drug use will be recorded, including non-prescription medication, complementary and alternative medications. Handling of missing date information for prior or concomitant medications is given in Section [7.11.2](#)

If the medication start date and end date are both missing, the medication will be counted as both previous and concomitant.

If the medication start date is missing and the end date is prior the date of first drug administration, the medication will be counted as previous medication.

If the medication start date is missing and the end date is after the date of first drug administration, the medication will be counted as concomitant medication.

6.5.4 Variables related to study drugs

Randomization/Treatment Arms

[Table 9](#) below presents the groups to which subjects are randomized under the initial protocol version 1.0.

Table 9 Randomization arms under Protocol version 1.0

Randomization Arm Code (OARMCD)	Correction Period	Maintenance period	Randomization Arm (OARM)
1A	TIW	QW	Roxadustat TIW/QW
1P	TIW	QW	Placebo TIW/QW
2A	TIW	BIW	Roxadustat TIW/BIW
2P	TIW	BIW	Placebo TIW/BIW
3A	TIW	TIW	Roxadustat TIW/TIW
3P	TIW	TIW	Placebo TIW/TIW

Table 10 below presents the groups to which subjects are randomized under protocol version 2.0 and later.

Table 10 Treatment arms under protocol version 2.0

Randomization Arm Code (ARMCD)	Randomization Arm (ARM)
A	Roxadustat
B	Placebo

For the statistical analysis, treatments will be pooled across placebo and roxadustat under both protocol versions.

Analysis date of First Dose Intake

Date of first study drug dose intake is collected in the Day 1 visit in the Randomization eCRF. In case of a missing/partial date, the earliest available date will be used. It will be on the same day than the randomization date and before the next dose date.

Analysis Date of Last Dose

Date of Last Study Drug Dose is collected at the End of Extended Treatment visit in the End of Extended Treatment eCRF. When this date is not known, all efforts should be made to obtain the date from the investigator. If it is still missing after all efforts have been made, then the visit date of the End of Extended Treatment Visit will be used as the Analysis Date of Last Dose. If subject is lost to follow-up and none of these dates are available then the date of the last available assessment during the study will be used.

If analysis date of last dose is missing due to fact that date of last dose is a partial date with day unknown (month and year populated), then minimum between the date of death and end of month for the partial date will be used.

Duration of exposure in days (overall)

For each subject, the Length of Time on treatment will be calculated in days, using the following formula:

$$(\text{'Analysis Date of Last Dose'} - \text{'Analysis Date first dose intake'}) + 1$$

Amount of Prescribed (planned) Medication

The number of milligrams prescribed at each visit (including unscheduled visits) is captured in the *Changes in Dosing* eCRF. The investigator reported dose and frequency will be used when available. When the investigator reported dose and frequency are not available, the IRS reported dose and frequency will be used.

The prescribed daily and weekly dose at each visit (including unscheduled visits) will be calculated as follows:

$$\text{Daily Prescribed dose in mg} = \frac{\text{Prescribed weekly Dose}}{7}$$

Prescribed weekly dose is defined as prescribed dose x 3 as the prescribed frequency is TIW for study drug for patients randomized following protocol amendment 2.0. For patients randomized prior protocol amendment 2.0, other prescribed frequencies may be entered in the eCRF and should be used for the calculation of the prescribed weekly dose.

Each visit will have an associated start and end date as follows:

- Each visit (including unscheduled) has an associated date. This is the start date.
- Each visit (including unscheduled) will have an associated end date. This date will be the date of the next consecutive visit [including unscheduled visits and EOT] minus 1 day. This is the end date.

Time periods of interest are defined below (monthly is defined as a period of 4 weeks or 28 days) as follows:

Table 11 Time periods of interest

Time Period	Analysis Start Day	Analysis End Day*
Week 4 (Month 1)	Day 1	Day 28
Week 8 (Month 2)	Day 29	Day 56
Week 12 (Month 3)	Day 57	Day 84
Week 16 (Month 4)	Day 85	Day 112
Week 20 (Month 5)	Day 113	Day 140
Etc....		
Week 104 (Month 26)	Day 701	Day 728
Overall Treatment Period	Day 1	End Day of Extended Treatment Period
Day 1 - Week 24	Day 1	End Day of Month 6 (day 168)
Day 1 – Week 36	Day 1	End Day of Month 9 (day 252)
Day 1 – Week 52	Day 1	End Day of Month 12 (day 364)

*or EOT whichever is first

**Extended treatment period only applies for subjects who do not discontinue prior to week 52.

This will allow us to calculate the amount of prescribed medication in a time period as the sum of the daily prescribed amount within the time windows defined above.

In addition, amount of prescribed medication in mg/kg will be calculated. To convert a dose given in mg into a dose in mg/kg, the body weight recorded at day 1 will be used.

Amount of Consumed Medication

The consumed Investigational Product Medication is captured in the *Study Drug Accountability* eCRF which includes the following kit information:

- Kit strength, kit treatment, kit dispensed, date of kit dispensed, kit strength total number of tablets dispensed
- Kit returned, returned date, total number of tablets returned

For each kit, the following will be calculated:

- Start Day of Exposure for each kit: study day kit dispensed
- End Day of Exposure for each kit: study day kit returned – 1 Day
- Amount dispensed for each kit: kit strength x number of tablets dispensed
- Amount returned for each kit: kit strength x number of tablets returned
- Amount consumed for each kit: amount dispensed – amount returned
- Daily consumed dose for each kit : amount consumed/(end day of exposure-start day of exposure +1)

The same methodology as described for Amount Prescribed (planned) Medication will apply to calculate amount of consumed medication for each time period by summing up the different daily consumed amount of the different kits on a given day (subjects will be dispensed more than one kit on a given visit).

In addition, amount of consumed medication in mg/kg will be calculated.

Compliance

Compliance will be calculated for the time periods defined in Amount of Prescribed (planned) Medication. Compliance in % will be calculated for each time period (not reported cumulatively) as:

$$\frac{\text{Amount consumed during time period}}{\text{Amount prescribed during time period}} \times 100$$

The following compliance categories will be defined:

- less than 50% (significant drug noncompliance)
- at least 50%, less than 75% (moderate drug noncompliance)
- at least 75%, less than 125% (acceptable compliance)
- greater or equal 125% (drug over compliance)
- unknown

Dose Changes

Dosing changes are collected in the Study Drug - Dosing Decisions eCRF.

- A dose change is the change in the number of milligrams on the dose per intake (for example from 200 mg to 250 mg).

For example a change from 200 TIW to 250 TIW is a change of 600 mg to 750 mg per week which is regarded as a change in intake dose.

For each subject the total number of dose changes will be calculated.

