5.3 Per Protocol Set (PPS)

The Per-Protocol Set includes all FAS subjects who do not meet any of the reasons to exclude a complete subject from PPS listed in [Table 3](#). This PPS will be used for all disposition, demography and baseline characteristics.

Table 3 Criteria for excluding a subject from PPS

Number	Reasons for exclusion from PPS
1	Subject who receives less than 2 weeks of study treatment.
2	Patient without a valid corresponding Hb. A valid corresponding Hb is defined as an Hb value from the central laboratory that is measured at least 2 weeks after the first dose and was either before the last study drug intake or at maximum three days after the last drug intake.
3	Prescribed study drug compliance during treatment < 75% during the first 24 weeks or until EOT, whatever comes first.
4	Violation of inclusion or exclusion criteria which may affect the assessment of the efficacy of the study drug during the reference period or until EOT, whatever comes first.
5	Subjects where breaking of the randomization code occurs during the reference period or until EOT, whatever comes first.
6	Administration of wrong randomization study drug for more than one week during the reference period or until EOT, whatever comes first
7	Administration of prohibited concomitant medication affecting efficacy listed in Appendix 12.1 of the protocol during the first 24 weeks or until EOT, whatever comes first.
8	Administration of rescue therapy significantly deviating from the protocol during the first 24 weeks or until EOT, whatever comes first.

More information on the derivation of these criteria can be found in the Classification Specifications.

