7.11.6 End of Efficacy Emergent Period

For all subjects, the end of Efficacy Emergent Period will be defined as :

- **Minimum (Analysis date of Last Dose + 7 days , EOT Visit)**

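### Compliance keeps accruing prescribed drug from a permanent stop to the day before the EOT visit, which can push a fully compliant early stopper below the 75% Per Protocol limit

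*SAP*

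**What the plan says.** SAP 6.5.4 defines compliance as amount consumed over amount prescribed, and states: "Compliance will be calculated for the time periods defined in Amount of Prescribed (planned) Medication".

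- **Denominator.** The prescribed amount is "the amount of prescribed medication in a time period as the sum of the daily prescribed amount within the time windows defined above". The daily amount is the prescribed weekly dose divided by 7, with three doses a week under protocol version 2.0. Each dosing record starts at its visit, and its end is fixed by this rule: "This date will be the date of the next consecutive visit [including unscheduled visits and EOT] minus 1 day". The footnote to Table 11 caps each period at its end day "or EOT whichever is first". The last dose appears in neither place.
- **Numerator.** "Amount consumed for each kit: amount dispensed – amount returned". That amount is spread evenly from the dispensing day to this limit: "End Day of Exposure for each kit: study day kit returned – 1 Day".
- **Use.** Criterion 3 in SAP Table 3 removes a subject from the PPS for "Prescribed study drug compliance during treatment < 75% during the first 24 weeks or until EOT, whatever comes first". The same ratio feeds the compliance tables of SAP 7.3.2.

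Elsewhere the SAP works from the last dose. Duration of exposure in 6.5.4 ends at the Analysis Date of Last Dose. PPS criterion 2 accepts a haemoglobin value only up to three days after the last intake. Section 7.11.6 ends the Efficacy Emergent Period at "Minimum (Analysis date of Last Dose + 7 days , EOT Visit"), so it treats the last dose and the EOT visit as separate dates.

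**The concern.** A subject who stops for good between visits and attends EOT later goes on accruing prescribed milligrams on days off drug. The ratio then mixes two things: how well the subject took the drug while on it, and how long the site took to arrange the EOT visit. Protocol footnote a to the Schedule of Assessments requires EOT visits after a premature stop but sets no maximum interval from the last dose.

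Stopping early is not one of the deviations listed in Protocol 8.1.6, and PPS criterion 1 already handles treatment shorter than two weeks. So criterion 3 could remove subjects just past that limit for a reason unrelated to adherence.

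At stake are the SAP 7.3.2 tables, the PPS on which hypertension noninferiority is judged, and the PPS repeats of both primary endpoints. Time to hypertension runs from first dose to at most 28 days after the last (SAP 6.1.2.7 and 6.2), so an early stopper contributes follow-up, and possibly an event, directly.

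**Working it through.** The plan states no compliance figure to reproduce, so I applied its rules to a model subject.

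**Inputs.** Three doses a week on Days 1, 3, 5, 8, 10, 12 and so on, all taken up to stop day L. Constant dose, so milligrams reduce to doses. All unused tablets returned by the EOT visit on day L + g. The gap g is my assumption, varied from 3 to 28 days. Visits in Weeks 1, 2, 4, 6 up to 24 (SAP Table 1), at target day 7 × week + 1 (SAP 7.11.4). Threshold 75%, window closing on Day 168.

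**Formula.** For EOT visits up to Day 169, compliance = doses taken ÷ [(EOT day − 1) × 3/7]. In calendar days this is roughly L/(L + g − 1), which is below 75% when L < 3(g − 1). Hence the rule of about one third.

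| Stop day | EOT day | Doses taken | Doses prescribed | Compliance |
|---|---|---|---|---|
| 15 | 29 | 7 | 28 × 3/7 = 12 | 58.3% |
| 17 | 29 | 8 | 12 | 66.7% |
| 26 | 40 | 12 | 39 × 3/7 = 16.71 | 71.8% |
| 29 | 43 | 13 | 42 × 3/7 = 18 | 72.2% |
| 33 | 47 | 15 | 46 × 3/7 = 19.71 | 76.1% |
| 37 | 51 | 16 | 50 × 3/7 = 21.43 | 74.7% |
| 54 | 68 | 24 | 67 × 3/7 = 28.71 | 83.6% |
| 54 | 82 | 24 | 81 × 3/7 = 34.71 | 69.1% |
| 79 | 107 | 34 | 106 × 3/7 = 45.43 | 74.8% |

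The Day 17 stop falls between the Week 2 and Week 4 visits, with EOT on the Week 4 target day.

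**Latest stop day below 75%, by gap:** 3 days, none; 7 days, Day 16; 14 days, Day 37; 21 days, Day 58; 28 days, Day 79. The approximation gives 18, 39, 60 and 81 for the last four. Not every earlier stop is caught: Day 33 with a 14-day gap stays at 76.1%.

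**EOT tied to the next scheduled visit.** On the target day, only stop Days 15–18 and 29–30 fall below 75%. Days 19–21 give 9/12, exactly 75%, and are kept. Two days after target, stop Days 15–21 and 29–32 fall below.

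**Stops after Week 24** barely matter for criterion 3. A stop on Day 175 with EOT on Day 197 gives 100% for the first 24 weeks.

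**Reading EOT as the last dose.** Ending only the denominator at the last dose still leaves a kit that straddles the stop diluted. Take stop Day 33 and EOT Day 47. The kit dispensed on Day 29 and returned on Day 43 holds 3 doses spread over 14 days, of which 5 fall by Day 33: 3 × 5/14 = 1.07. Compliance is (12 + 1.07) ÷ (33 × 3/7 = 14.14) = 92.4%. Ending the kit at Day 33 as well gives 15/14.14 = 106.1%.

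**After correction.** Stop Day 15 covers Days 15–16: 7 ÷ (16 × 3/7) = 102.1%. Stop Day 19 covers Days 19–21: 9 ÷ (21 × 3/7) = 100%. Without the covered days these are 7 ÷ (15 × 3/7) = 108.9% and 9 ÷ (19 × 3/7) = 110.5%. Across the stop days checked from 15 to 166, the uncovered figure is about 101% to 111%.

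**The case against.** The best defence is that other SAP text ties compliance to actual treatment. Section 7.3.2 limits overall compliance to subjects whose first and last treatment days are known. Criterion 3 speaks of compliance during treatment, and the key terms define the treatment period as ending at the last intake. EOT abbreviates End of Treatment, and the SAP elsewhere writes EOT Visit when it means the visit. This makes another reading possible. It does not displace 6.5.4, where EOT stands in a list of visits that close an interval, and it leaves the kit rule untouched.

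Two further points stand. Prescribed dose is captured at every visit, including unscheduled ones, so a stop recorded there as a zero dose would remove the effect. The Day 15 and Day 29 rows, being stops on visit days, assume no such entry; the Day 17 row does not fall on a scheduled visit. Also, SAP 5.3 refers the derivation of the PPS criteria to the Classification Specifications, which may settle this.

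A reader might infer more than the documents support:

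- That fully compliant early stoppers are removed as a class. They are not: a prompt EOT visit or a later stop keeps them above 75%.
- That the SAP expects gaps above 7 days. Section 7.11.6 allows for one but does not show that it is common.
- That the PPS response rate is inflated, or one arm favoured. Stopping before response does count as non-response (SAP 6.1.1.1), but the documents give no stopping pattern, gap or response status by arm for these subjects.

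**Conclusion.** The point holds as a defect in a stated rule, with limited reach. As written, off-drug days before EOT count as non-compliance, so final-period compliance is understated for anyone with more than a few days between last dose and EOT. Exclusion of a fully compliant subject needs a gap above about one third of the time on drug: stops to about Day 37 for 14 days, about Day 79 for 28 days, none for 3 days. This assumes three-times-weekly dosing, every dose taken, no zero dose recorded at the stop, and no contrary rule in the Classification Specifications. The gap itself is assumed.

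The consequences are modest. MAP noninferiority is little affected: the Week 20 window opens on Day 141 − 7 = 134, while a Day 79 stopper's Safety Emergent Period ends by Day 79 + 28 = 107. Hypertension noninferiority is more exposed, but SAP Table 16 takes both tests out of the hierarchy. Both are repeated on All Randomized, and hypertension also on the FAS. For the primary endpoints the PPS is a sensitivity set without hypothesis testing. The number of subjects affected, and the direction by arm, cannot be determined from the documents.

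**What to change.** In SAP 6.5.4, end the last prescribed interval at the earlier of (a) the next visit minus 1 day and (b) the Analysis Date of Last Dose plus the days that dose covers under the prescribed frequency. End the last kit's exposure in the same way, with the return day minus 1 in place of (a). Say how a permanent stop before EOT is entered in the dosing record. Apply PPS criterion 3 to the corrected ratio and align the Classification Specifications.

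If the covered days are left out, compliant subjects score about 101% to 111%. That is untidy but inside the SAP's acceptable band, which runs from 75% to just under 125%.

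The cost is a short text edit and a small change to two derivations, before database hard lock. The last-dose date is already derived. Where it is missing and the EOT visit date is substituted (SAP 6.5.4), the correction changes little.
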